4.3.5.5 Other exploratory endpoint analysis

- The average monthly IV iron use during Week 0 to 36 and week 28 to 36 will be compared between the two treatment groups analogously as the secondary efficacy endpoint of IV iron.
- Average monthly IV iron usage per PEY per arm will be reported descriptively.
- Mean change in heart rate from baseline throughout week 28 to the EOT visit. For each subject, the change from baseline to the mean level across all heart rate values from week 28 until the EOT visit will be used as the dependent variable. An ANCOVA approach will be used with baseline heart rate, baseline Hb as covariates and the treatment groups, CV history, geographic region and dialysis duration as fixed effects.

- Change in blood pressure (DBP, SBP and MAP) from baseline throughout week 28 to the EOT visit. Analysis will be conducted using ANCOVA analogously as the analysis of change in heart rate.
- Iron parameters: Serum iron, TIBC, Ferritin and TSAT level at each testing time-point and mean change from baseline throughout week 28 to the EOT visit. For each of the serum profiles, analysis will be conducted using ANCOVA analogously as the analysis of change in heart rate.
- Change in variables concerning lipids: Total cholesterol, LDL, HDL and triglyceride. For each of the lipids, analysis will be conducted using ANCOVA analogously as the analysis of change in heart rate, from week 24 to the EOT visit. Percent of subjects who achieved target LDL level <100 mg/dL will also be compared at all available time points
- The usage of statins, types of statins and statin dose levels will be reported descriptively.
- Subject initiation of ESA therapy post study drug discontinuation will be reported descriptively.
- Change from baseline in hepcidin to week 24. Analysis will be conducted using ANCOVA analogously as the analysis of change in heart rate.

4.3.6 Sensitivity analysis of efficacy endpoints

- The analysis of the primary efficacy endpoint for US will be repeated but will exclude Hb values 6 weeks after the use of rescue therapy. ITT analysis set will be used.
- The analyses of primary efficacy endpoint and the secondary efficacy endpoints will be repeated using the OT+7.
- The analysis of the US primary efficacy endpoint and the Hb related secondary efficacy endpoints will be repeated using the PPS.
- The secondary endpoint of RBC transfusion as rescue therapy will be repeated using the ITT analysis set.
- Change in Hb from baseline using MMRM. Mean change from baseline across all Hb values from week 28 to week 52 will be analysed using baseline Hb as a covariate and treatment group, visit, visit by treatment interaction, CV history, geographic region and dialysis duration as fixed effects. ITT analysis set will be used.

- Proportion of total time of interpolated Hb within the interval of 10-12 g/dL from week 28 to the EOT visit. The difference between roxadustat and epoetin alfa will be compared using an ANCOVA model with baseline Hb as a covariate, and CV history, geographic region and dialysis duration, as fixed effects. ITT analysis set will be used.
- Change in Hb from baseline using PMM – Last Mean Carried Forward, as specified in Section 4.2.8.1. ITT analysis set will be used.
- Change in Hb from baseline using PMM – PMM – Baseline Mean Carried Forward (ANCOVA), as specified in Section 4.2.8.2. ITT analysis set will be used.
- Change in Hb from baseline using PMM – Baseline Mean Carried Forward for roxadustat subjects, MAR assumption for epoetin alfa group (ANCOVA), as specified in Section 4.2.8.2. ITT analysis set will be used.

4.3.7 Subgroup analyses

Subgroup analysis will be performed for both the primary efficacy endpoints of Hb, with the ITT analysis set for the primary endpoint for US and the PPS for the primary endpoint for EU.

- Age: <65 and ≥ 65 ; <75 and ≥ 75 years
- Gender: Male vs Female
- Race: White, Black or African American, Asian, Native Hawaiian or other Pacific Islander, American Indian or Alaska native, other
- Weight: <70 kg vs ≥ 70 kg; and <100 kg vs ≥ 100 kg
- Weight by gender-specific median (4 groups)
- Body mass index (BMI): <30 and ≥ 30 kg/m²
- Geographical region: US vs Ex-US
- Geographical region:
 - North America
 - South America
 - Asia and Australia
 - Europe
- Peritoneal dialysis vs. Hemodialysis

- Cardiovascular/cerebrovascular/thromboembolic history: Yes or No
- Baseline Hb value: $\leq 10.5\text{g/dL}$ and $>10.5\text{g/dL}$
- Incident vs stable dialysis: dialysis duration ≤ 4 months vs >4 months from the randomization date
- Diabetes history: Yes vs No
- Epoetin alfa dose prior to randomization: $\leq 12,500$ IU/week and $>12,500$ IU/week
- Baseline hsCRP (\leq ULN vs $>$ ULN).

4.3.8 Safety assessment analysis

The safety analysis will be performed using the OT+7. Safety variables include adverse events (AE), laboratory variables, vital signs, ECG variables and physical examinations. For each safety variable, the last assessment made on the screening visits or the randomization visit will be used as the baseline for all analyses, unless specified otherwise.

4.3.8.1 Adverse events

Adverse events will be coded using the Medical Dictionary for Regulatory Activities (MedDRA) version 20.0 higher.

An AE (classified by preferred term) started during the treatment period will be considered a treatment-emergent adverse event (TEAE) if it was not present prior to the first dose of study medication. An AE that starts more than 7 days after the last dose of study medication will not be counted as a TEAE.

The number, percentage and percentage per PEY of subjects reporting TEAEs in each treatment group will be tabulated by system organ class and preferred term; by system organ class; by preferred term and by system organ class, preferred term, and relationship to study medication. If more than one event occurs with the same preferred term for the same subject, the subject will be counted only once for that preferred term using the most severe and most related occurrence for the summarization by severity and by relationship to the study medication. In addition to reporting TEAEs by number of subjects, the table by system organ class and preferred term will also be reported by patient years and event rates. Thus, allowing for potential systematic differences in mean exposure between the treatment groups. The event rate for a particular AE will be derived as the number of subjects with the AE, divided by total number of days at risk for the AE across all subjects in given group, multiplied by 365.25 multiplied by 100.

The distribution of TEAEs by severity and relationship to study medication will be summarized by treatment group.

The incidence of common ($\geq 5\%$ of subjects in any treatment group) TEAEs, common treatment-emergent serious AEs (TESAE), and AEs leading to discontinuation of study medication will be summarized by preferred term and treatment group, sorted in decreasing overall (across treatments) frequency. Moreover, TEAEs leading to hospitalization by system organ class and preferred term will be presented. In addition, related deaths and fatal SAEs (i.e., events that caused death) will be summarized separately by treatment group, system organ class and preferred term. TEAEs with outcome of deaths and TESAEs will also be presented for the ITT analysis set.

TEAEs and TESAEs by system organ class and preferred term will also be reported with OT+3 and OT+0.

Listings will be presented of subjects with serious adverse events (SAEs), subjects with adverse events leading to discontinuation, and subjects who died.

4.3.8.2 Laboratory variables

Descriptive statistics for laboratory values and mean percent changes from baseline at each assessment time point will be presented by treatment group for the following laboratory variables collected in the study:

- Hematology: Hemoglobin, hematocrit, RBC count, MCV, MCH, MCHC, WBC count, WBC differential, platelet counts and Reticulocyte count
- Chemistry: Alkaline phosphatase, ALT, AST, total bilirubin, LDH, total protein, albumin, fasting glucose, phosphate, uric acid, BUN, creatinine, sodium, and potassium.
- Serum iron, ferritin, TIBC, TSAT
- CHr
- Hepcidin and hsCRP

The laboratory values will be presented in SI units, except for Hb, ALT, AST, ALP and Gamma Glutamyl Transferase, which will be presented in conventional units

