5.2.2 Laboratory assessments

Blood samples for determination of clinical chemistry, hematology, lipid panel, serology, vitamin B12, folate and serum iron profile will be taken at the times indicated in [Table 1](#) and analyzed by Covance Central Laboratory Services.

Additional safety samples may be collected if clinically indicated at the discretion of the Investigator.

The following laboratory variables will be measured (blood, serum or plasma will be specified in the laboratory manual):

Table 2 Laboratory Safety Variables

Hematology/Hemostasis	Clinical Chemistry
Hemoglobin (Hb)	Creatinine
Hematocrit	Creatinine kinase
Leukocyte count	Bilirubin, total
Leukocyte differential count (absolute count)	Alkaline phosphatase (ALP)
Platelet count	Aspartate aminotransferase (AST)
	Alanine aminotransferase (ALT)
Serology	Gamma-glutamyl transferase (GGT)
Hepatitis B surface antigen	Albumin
Hepatitis C antibody	Potassium
Human immunodeficiency virus (HIV)	Calcium, total
	Sodium
Additional Laboratory Analyses	Chloride
Vitamin B12	Magnesium
Folate	Bicarbonate
Intact Parathyroid hormone (iPTH)	Phosphorus
hsCRP*, hepcidin*	Glucose
Lipid Panel	Uric Acid

Total cholesterol

HDL

Triglycerides

Calculated low-density lipoprotein (LDL)

Total protein

Lactate dehydrogenase

Blood urea nitrogen

Serum hCG pregnancy test

Iron Profile

Iron

Ferritin

Total iron binding capacity (TIBC)

Transferrin saturation (TSAT)

* = will be analysed from specimens obtained in subjects who consent to biobanking blood samples

The Investigator should make an assessment of the available results with regard to clinically relevant abnormalities. The laboratory results should be signed and dated and retained at centre as source data for laboratory variables. For information on how AEs based on laboratory tests should be recorded and reported, see Section 6.3.

Note: In case a patient shows an AST **or** ALT $\geq 3 \times \text{ULN}$ **or** total bilirubin $\geq 2 \times \text{ULN}$ please refer to [Appendix D](#) ‘Actions required in cases of combined increase of Aminotransferase and Total Bilirubin - Hy’s Law’, for further instructions.

Additional laboratory assessments performed for purposes other than general safety evaluation are also listed in [Table 2](#)

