6.3.6 Adverse events based on examinations and tests

The results from protocol mandated laboratory tests and vital signs will be summarised in the clinical study report. Deterioration as compared to baseline in protocol-mandated laboratory values, vital signs should therefore only be reported as AEs if they fulfil any of the SAE criteria or are the reason for discontinuation of treatment with the investigational product.

If deterioration in a laboratory value/vital sign is associated with clinical signs and symptoms, the sign or symptom will be reported as an AE and the associated laboratory result/vital sign will be considered as additional information. Wherever possible the reporting Investigator uses the clinical, rather than the laboratory term (e.g. anemia versus low hemoglobin value). In the absence of clinical signs or symptoms, clinically relevant deteriorations in non-mandated parameters should be reported as AE(s).

Deterioration of a laboratory value, which is unequivocally due to disease progression, should not be reported as an AE/SAE.

Any new or aggravated clinically relevant abnormal medical finding at a physical examination as compared with the baseline assessment will be reported as an AE.

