6.3.7 Liver enzymes

If a patient meets any of the following criteria, please refer to [Appendix D](#) for further instruction: $AST \geq 3x$ ULN, $ALT \geq 3x$ ULN, total bilirubin $\geq 2x$ ULN.

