7.2.3.3 Roxadustat dose adjustments

Roxadustat dose will remain constant during the first 4 weeks of the treatment period, unless a dose reduction is required for excessive erythropoiesis. Dose may be adjusted at week 4 and every 4 weeks thereafter in accordance b to achieve and maintain Hb 11±1 g/dL. Dose adjustment is based on Hb assessed by Hemocue.

Table 6 Roxadustat dose adjustments

Changes in Hb over past 4 weeks	Hb <10.5g/dL	Hb 10.5 to 11.9g/dL	Hb 12.0 to 12.9g/dL	Hb ≥13.0g/dL
<-1.0	↑	↑	No change	Hold, then resume dosing when Hb ≤11.9 g/dL, at a dose that is reduced by two dose steps
-1.0 to 1.0	↑	No change	↓	
>1.0	No change	↓	↓	

Dose Increases and Reductions:
Dose increases (↑) and reductions (↓) are pre-set according to dose steps.
The dose steps are as follows: 20, 40, 50, 70, 100, 150, 200, 250, 300, and 400 mg.

Example: A dose increase at a dose of 70 mg results in 100 mg as the new dose. A dose reduction at a dose 150 mg results in 100 mg as the new dose.

If patients on 20 mg TIW need dose reduction, change frequency to twice a week, i.e. 20 mg administered twice a week. If further dose reduction is needed, reduce frequency to once weekly, i.e. 20 mg administered once a week.
Note: Maximum dose is capped at the lower of 3.0 mg/kg or 400 mg per dose administration.

Dose Adjustment for Excessive Erythroipoiesis:

- If Hb increases by >2.0 g/dL within a 4 week period, the dose should be reduced by one dose step.

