7.7.1.1 Statins

When coadministered with roxadustat, hydroxymethylglutaryl coenzyme A reductase inhibitor (statin) exposure was increased 2- to 3-fold. For patients randomized to roxadustat, investigators should consider this interaction and local prescribing information when deciding on the appropriate statin dose for individual patients, bearing in mind the impact of ethnicity, other concomitant medications, renal and hepatic function. Goals of lipid lowering treatment should be maintained as clinically indicated. The recommended maximum daily statin doses are: simvastatin 20 mg, atorvastatin 40 mg, rosuvastatin 10 mg, pravastatin 40 mg, fluvastatin 40 mg (20 mg if eGFR<30), pitavastatin 2 mg (1 mg if eGFR<30).

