3.2 Safety assessments

Safety will be further assessed by evaluating the following:

- Occurrence of treatment emergent adverse events (TEAEs) and treatment emergent serious adverse events (TESAEs)
- Changes from baseline in vital signs and physical examinations.
- Mean change from baseline in clinical laboratory values.
- Occurrence of clinically significant changes from baseline in vital signs and ECG values.

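### Non-serious, asymptomatic laboratory outliers that do not stop treatment have no planned by-arm count, and six collected chemistry tests are missing from the SAP summary list

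*SAP*

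**What the plan says.** Protocol 6.3.6 sets the rule. It states that "The results from protocol mandated laboratory tests and vital signs will be summarised in the clinical study report", and on that ground says that deteriorations in those tests "should therefore only be reported as AEs if they fulfil any of the SAE criteria" or if they are the reason for stopping study drug. Signs or symptoms that accompany a deterioration are reported as AEs. Clinically relevant deteriorations in tests the protocol does not mandate are also AEs.

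The SAP then describes the summary. SAP 3.2 lists, for laboratory data, "Mean change from baseline in clinical laboratory values"; its item on clinically significant changes covers vital signs and ECG only. SAP 4.3.8.2 gives the tables: "Descriptive statistics for laboratory values and mean percent changes from baseline at each assessment time point will be presented by treatment group". It sets no limits and plans no shift table. SAP 4.3.8.3 and 4.3.8.4 do set limits for vital signs and ECG, and tabulate subjects beyond them by arm.

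The protocol has laboratory limits of its own. Section 6.3.7 opens with "If a patient meets any of the following criteria" and names ALT or AST at 3 times ULN or more and bilirubin at 2 times ULN or more. Table 6 in Section 7.2.3.3 says "If Hb increases by >2.0 g/dL within a 4 week period, the dose should be reduced by one dose step", and SAP 1.2.1 uses the same change to define excessive erythropoiesis, in text that covers both arms. Table 2 in protocol 5.2.2 includes "Creatinine kinase" (evidently creatine kinase), and Section 7.7.1.1 says of statins given with roxadustat that "exposure was increased 2- to 3-fold".

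**The concern.** The study-report summary is the protocol's stated reason for narrowing AE capture, so it should show what the AE tables leave out. Liver-test elevations, muscle-enzyme elevations and rapid Hb rises happen in a few subjects at scattered times. Per-visit means respond weakly to them. A maximum shows one subject, not how many crossed a limit or whether ALT and bilirubin rose in the same subject.

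At stake is whether the report can show a difference between arms in subjects crossing limits the protocol itself treats as alerts. Two features add weight:

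- Protocol 1.2.4 names over-rapid Hb rise as a possible contributor to CV risk and says the dosing regimen minimises it. No planned analysis checks that.
- The SAP reports statin use descriptively but does not summarise the muscle enzyme collected alongside it.

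**Working it through.** The plan states no figure to reproduce here. The check is a comparison of texts, followed by an illustration.

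**Step 1. Where each kind of finding is counted by arm.**

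| Finding | Planned by-arm summary | Source |
|---|---|---|
| Serious, or stops treatment | AE tables | Protocol 6.3.6; SAP 4.3.8.1 |
| With signs or symptoms | AE tables, as the sign or symptom | Protocol 6.3.6; SAP 4.3.8.1 |
| Agreed Hy's Law case, or potential case unresolved after 3 weeks | SAE, so the serious TEAE tables | Protocol Appendix D, section 5; SAP 4.3.8.1 |
| Potential Hy's Law case with an agreed explanation that is not an AE | None; recorded on the CRF | Appendix D, section 5 |
| ALT, AST or bilirubin over its limit without meeting potential Hy's Law | None; alert, notification, follow-up | Protocol 6.3.7; Appendix D, sections 3 and 4.1 |
| Hb level of 13 g/dL or more | Share of exposure time (exploratory) | SAP 3.1.6.1 |
| Hb rise above 2.0 g/dL in 4 weeks | None | SAP 1.2.1; protocol Table 6 |
| Creatine kinase | None, not even a mean | Protocol Table 2; SAP 4.3.8.2 |
| Vital signs or ECG beyond limits | Number and percentage of subjects | SAP 4.3.8.3, 4.3.8.4 |

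**Step 2. Analyte lists.** Leaving out the pregnancy test, the chemistry column of protocol Table 2 has 20 analytes. The SAP 4.3.8.2 chemistry list has 14, all of them in Table 2 (reading phosphate as phosphorus). The difference is 20 − 14 = 6: creatine kinase, GGT, calcium, chloride, magnesium and bicarbonate. GGT appears in 4.3.8.2 only in the sentence on units. SAP Section 6 declares no change of analysis from protocol version 8.0.

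**Step 3. How far outliers move a mean (illustration; every input is assumed).** Take n = 1000 per arm, about half of the planned 2000, all tested at every visit. If k subjects have a percent change c at a visit, the visit mean moves by k × c / n.

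- Let 20 subjects (2%) each have one ALT rise from 20 to 120 U/L, which is 3 times an assumed ULN of 40. The change is (120 − 20)/20 = 500%.
- Spread over 40 visits, that is 20/40 = 0.5 subjects per visit. The shift is 0.5 × 500 / 1000 = 0.25 percentage points.
- If all 20 fell at one visit, the shift there would be 20 × 500 / 1000 = 10 points.
- In between, 10 subjects with a 300% change at one visit give 10 × 300 / 1000 = 3.0 points.

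The standard error of the between-arm difference is SD × √(2/n). With an assumed SD of percent change from 30 to 70 points, it runs from 30 × √0.002 = 1.34 to 70 × √0.002 = 3.13 points. The spread-out case (0.25) is far below this range. The 3.0-point case lies between 3.0/3.13 = 1.0 and 3.0/1.34 = 2.2 standard errors. The fully clustered case (10) would show in the mean, though still without saying how many subjects caused it. A threshold table would show 20 against, say, 5 subjects (2% against 0.5%) in every case.

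**The case against.** A reader might infer that these outliers are counted nowhere. The documents do not support that. Agreed Hy's Law cases must be reported as SAEs even when no other serious criterion applies, and so must potential cases left unresolved after 3 weeks. Symptomatic muscle injury would be reported through its symptoms. Overshoot in Hb level is covered by exposure time in bands up to 13 g/dL and above. SAP 4.1 includes minimum and maximum and lists all study data by subject, and the DSMB sees unblinded data during the trial. All of this stands, and it narrows the gap.

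Nor does the SAP break protocol 6.3.6 by summarising with means: that section promises a summary, not threshold counts. Only the six missing analytes are a mismatch with it. The stray mention of GGT suggests loose drafting rather than deliberate exclusion. Musculoskeletal pain should not be pressed either: protocol 1.3 reports it at high doses in healthy subjects and says it was not seen at usual therapeutic doses in the Phase 2 target populations.

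The remaining replies are weaker. Listings for about 2000 subjects are not a comparison between arms. Time at a high Hb level does not measure rate of rise. Whether a potential Hy's Law case has another explanation is agreed between the investigator and the sponsor in an open-label trial, which makes an objective count more useful. The pooled SAP is not among the documents; SAP 4.3.1 refers to it for CV safety, so laboratory outlier tables there can be neither confirmed nor excluded.

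**Conclusion.** The point holds within limits. Non-serious, asymptomatic deteriorations in mandated tests that do not stop treatment have no planned by-arm count. The specific gaps are isolated ALT, AST or bilirubin elevations, potential Hy's Law cases given a non-AE explanation, and Hb rises above 2.0 g/dL in 4 weeks. Six of 20 chemistry analytes have no planned summary.

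The text comparison needs no assumption. The size does: the visit-mean shift for 20 affected subjects runs from 0.25 to 10 points depending on how the rises cluster, and the 2% against 0.5% contrast is an illustration without basis in the documents. Nothing here suggests that such an imbalance exists. No primary estimate or error rate is affected. It is a gap in descriptive safety reporting, worth closing because closing it is cheap.

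**What to change.** In SAP 4.3.8.2:

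- Add creatine kinase, GGT, calcium, chloride, magnesium and bicarbonate to the chemistry list.
- On the OT+7 set, tabulate by arm the number and percent of subjects, and the rate per patient-exposure-year, with any post-baseline ALT or AST of at least 3 times ULN, total bilirubin of at least 2 times ULN, and both (the Appendix D definition of potential Hy's Law, which sets no time window between the two).
- For creatine kinase, add a shift table from baseline to worst value relative to ULN, overall and by statin use. The documents give no creatine kinase cut-off, and this table needs none beyond ULN.
- Count subjects with an Hb rise above 2.0 g/dL within 4 weeks, as defined in SAP 1.2.1. State whether central-laboratory or Hemocue values are used, because dosing follows Hemocue and efficacy follows the central laboratory, so the two counts need not agree. Show results with and without rises that follow an RBC transfusion.

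The cost is a few extra descriptive tables and their programming, from data already collected. Dosing, visits and the testing sequence do not change.

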2.2 Secondary objectives

Secondary Efficacy Objectives:	Outcome Measure:
The efficacy of roxadustat as compared to epoetin alfa based on Hb response and level during the study	
Proportion of total time of Hb \geq 10 g/dL from week 28 to week 52.
 
Proportion of total time of Hb within the interval of 10-12 g/dL from week 28 to week 52

The effect of roxadustat on Low-density lipoprotein (LDL) cholesterol as compared to epoetin alfa	Mean change from baseline in LDL cholesterol from baseline to week 24
The efficacy of roxadustat based on Hb response in inflamed subjects	Mean change in Hb from baseline to the subjects mean level between week 28 to week 52 in subjects with baseline high-sensitivity C-reactive protein (hsCRP) greater than the Upper Limit Normal (ULN)
The need for IV iron use in subjects treated with roxadustat as compared to epoetin alfa	Average monthly IV iron use

Secondary Efficacy Objectives:	Outcome Measure:
The need for RBC transfusion as rescue therapy in subjects treated with roxadustat as compared to epoetin alfa	Time-to-first (and proportion of subjects receiving) administration of red blood cell (RBC) transfusion as rescue therapy

Secondary Safety Objectives:	Outcome Measure:
To evaluate the safety and tolerability of roxadustat.	Adverse events (AEs), serious adverse events (SAEs). Changes in vital signs, electrocardiogram (ECG) and laboratory values.

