4.3.8.3 Vital signs

Blood pressure baselines are defined as the average of all measurements from the screening visits and randomization visit. For subjects on hemodialysis, vital signs should be recorded pre-dialysis. For subjects on peritoneal dialysis, vital signs may be recorded at any time during the visit.

Descriptive statistics for vital signs (e.g., systolic and diastolic blood pressure and MAP) and their changes from baseline at each visit and at the end of study will be presented by treatment group.

Vital sign values are potentially clinically significant (PCS) if they meet both the observed value criteria and the change from baseline criteria listed in [Table 2](#) below. The number and percentage of subjects with post-baseline PCS values will be tabulated by treatment group.

Table 2 Criteria for Potentially Clinically Significant Vital Signs

Vital Sign Parameter	Flag	Criteria*	
		Observed Value	Change
Systolic Blood Pressure (mmHg)	High	≥ 170	Increase of ≥ 20
	Low	≤ 90	Decrease of ≥ 20
Diastolic Blood Pressure (mmHg)	High	≥ 110	Increase of ≥ 15
	Low	≤ 45	Decrease of ≥ 15
Pulse Rate (bpm)	High	≥ 120	Increase of ≥ 20
	Low	≤ 50	Decrease of ≥ 20

* A post-baseline pre-dialysis or post-dialysis value is considered as a PCS value if it meets both criteria for observed value and change from pre-dialysis or post-dialysis baseline

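### SAP 4.3.8.2 summarises laboratory change as mean percent change where SAP 3.2 names mean change; the percent scale reads too high for analytes that vary widely within subjects and is undefined at a zero differential count (minor)

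*SAP*

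**What the plan says.** Three places describe how laboratory change is to be reported.

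- Protocol 2.2 gives the secondary safety outcome as "Changes in vital signs, electrocardiogram (ECG) and laboratory values". It does not state the scale.
- SAP 3.2 lists the laboratory safety variable as "Mean change from baseline in clinical laboratory values".
- SAP 4.3.8.2 plans: "Descriptive statistics for laboratory values and mean percent changes from baseline at each assessment time point will be presented by treatment group". The analytes that follow include ALT, AST, bilirubin, ferritin, "Hepcidin and hsCRP", and "WBC count, WBC differential, platelet counts and Reticulocyte count". Absolute change is not mentioned.

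The neighbouring section on vital signs (SAP 4.3.8.3) uses plain change: "and their changes from baseline at each visit and at the end of study will be presented by treatment group". The denominator of the percent change is a single value, since under SAP 4.3.8 "the last assessment made on the screening visits or the randomization visit will be used as the baseline for all analyses" unless specified otherwise. Protocol 5.2.2, Table 2, collects the leukocyte differential as absolute counts.

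The laboratory section has no log transformation, no geometric mean, and no rule for a baseline that is zero or below the quantification limit. SAP 6 declares no change from protocol version 8.0, and Table 4 in SAP 6.1 does not mention the laboratory scale.

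**The concern.** SAP 3.2 and SAP 4.3.8.2 name different statistics for the same variable, and a programmer following 4.3.8.2 would not produce the one in 3.2.

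The statistic in 4.3.8.2 is also the weaker of the two. A percent change cannot fall below −100% but has no upper limit, so a subject who happens to be low at baseline contributes a very large positive value. Because the baseline is one measurement, its noise enters the ratio in full. Averaged over subjects, this produces an apparent rise when nothing has changed, and it can turn a true fall into an apparent rise. For the rarer cell types in the differential, a zero baseline is realistic. The percentage then does not exist, and because SAP 4.1 summarises continuous variables on non-missing observations, the subject drops out of that row.

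These tables carry some weight for safety. Under Protocol 6.3.6, a deterioration in a mandated laboratory value is reported as an adverse event only if it meets a seriousness criterion or leads to discontinuation (an associated sign or symptom is reported in its own right), on the ground that the results are summarised in the study report. SAP 4.3.8.2 defines no shift table or threshold count for laboratory values, whereas vital signs and ECG have threshold tables (SAP Tables 2 and 3).

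**Working it through.** The documents state no figure for laboratory summaries, so there is nothing of the plan's own to reproduce. The check is a model calculation.

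**Inputs.** From the documents: the statistic (SAP 4.3.8.2), the single-value baseline (SAP 4.3.8), the ferritin entry floor of 100 ng/mL (Protocol 3.1, criterion 5), and about 2000 subjects randomised 1:1, hence about 1000 per arm (Protocol 8.2). Assumed: the within-subject log-scale SD, s, taken from 0.1 to 1.0.

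**Model with no true change.** For one subject, log X0 = m + e0 and log X1 = m + e1, with e0 and e1 independent normal errors of SD s. The subject's own level m cancels:

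- X1/X0 = exp(e1 − e0), and e1 − e0 has variance 2s².
- E[X1/X0] = exp(2s²/2) = exp(s²).
- Expected percent change = 100 × (exp(s²) − 1).

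In the same model the median percent change, the expected absolute change and the log geometric mean ratio are all zero. Simulation with 2,000,000 pairs per value of s agreed with the formula to within 0.2 percentage points.

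| s (assumed) | Mean % change, no true change | Mean % change, true 20% fall: 0.8·exp(s²) − 1 |
|---|---|---|
| 0.1 | +1.0% | |
| 0.2 | +4.1% | |
| 0.3 | +9.4% | −12.5% |
| 0.5 | +28.4% | +2.7% |
| 0.8 | +89.6% | +51.7% |
| 1.0 | +171.8% | |

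A true 20% fall appears as a rise only when 0.8·exp(s²) > 1, that is s² > ln(1.25) = 0.223, or s above about 0.47.

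**Ferritin with the entry floor.** Suppose the baseline value itself must be at least 100 ng/mL, with an assumed median of 400 ng/mL and between-subject log SD of 0.6. Simulated mean percent change is then +3.8%, +8.6%, +15.4% and +23.8% at s = 0.2, 0.3, 0.4 and 0.5. Selection at entry also moves the other summaries slightly, by regression to the mean: absolute change −0.3 to −4.0 ng/mL and median percent change −0.2% to −2.5% over the same range. If eligibility rests on a different sample from the baseline, the percent-change bias returns to the unrestricted values (+4.1% to +28.4%).

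**Between arms.** With equal s in both arms and 1000 subjects per arm, the simulated difference in mean percent change averaged about 0. Its SD was 2.2 percentage points at s = 0.3 and 13.7 at s = 0.8. With unequal s the bias does not cancel: s = 0.3 in one arm and 0.5 in the other gives 28.4 − 9.4 = 19.0 percentage points of false difference. That pair of values is illustrative only.

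**The case against.** The strongest reply is that little depends on this statistic, and much of it stands.

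- **Other summaries exist.** SAP 4.3.8.2 also plans descriptive statistics of the values themselves, and SAP 4.1 includes the median and range as appropriate. A flat median beside a positive mean percent change would expose the artefact. This holds, but medians are conditional, and subtracting visit means does not give paired change when subjects miss visits.
- **Absolute change is analysed for some analytes.** SAP 4.3.5.5 covers change in the iron indices, including ferritin, and in hepcidin by ANCOVA. This is real mitigation. Those analyses are exploratory, use the ITT set by default (SAP 4.3.5) and are not the by-visit safety tables on OT+7. They do not cover ALT, AST, bilirubin or hsCRP.
- **No decision rests on the table.** SAP 4.2.2 treats everything outside the confirmatory sequence as descriptive. Liver safety is followed subject by subject through the threshold rules in Protocol 6.3.7 and Appendix D, which this statistic does not affect. hsCRP and hepcidin come from optional samples at randomization and week 24 only (Protocol Table 1). All of this stands, and it is why the point is minor.

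A reader might infer that hsCRP, hepcidin, ferritin and ALT will all show large false increases. The documents do not support that. They give no within-subject variability for any analyte, and at s of 0.2 or below the bias is at most about 4%. A reader might also infer a distorted comparison between arms. That needs unequal variability. IV iron is restricted on roxadustat and given by standard of care on epoetin alfa (Protocol 7.7.3), which makes unequal variability conceivable for iron indices, but no figure supports it. Nor is a zero baseline a concern for ferritin, given the entry floor. For hsCRP and hepcidin the related question is how values below the quantification limit are handled.

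**Conclusion.** The point holds as a minor one. SAP 3.2 and SAP 4.3.8.2 disagree on the laboratory change statistic. The conflict lies within the SAP, because the protocol leaves the scale open. Followed as written, 4.3.8.2 gives a change summary that is biased upward for right-skewed analytes with high within-subject variability, and it has no rule for a zero baseline in the differential counts.

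The size rests on an assumed s, a log-normal model and independent errors at the two visits; positively correlated errors would make it smaller. The bias may be material for highly variable analytes, plausibly hsCRP and hepcidin as an assumption, and may be only a few percent for ferritin and ALT. It appears within each arm and largely cancels between arms if variability is equal. No confirmatory test, error rate, power or sample size is affected. What keeps it worth fixing is that ALT, AST, bilirubin and hsCRP have no other change analysis and no threshold count in the SAP.

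**What to change.** In SAP 4.3.8.2:

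1. Replace mean percent change with absolute change from baseline by visit and treatment group (mean, SD, median), so that it agrees with SAP 3.2.
2. For skewed analytes (hsCRP, hepcidin, ferritin, ALT, AST, alkaline phosphatase, bilirubin), add either the geometric mean ratio to baseline or the median percent change.
3. State how zero and below-quantification values are handled. The geometric mean ratio needs this rule too, since it also fails at zero.
4. Do not compute percent change for differential counts.

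The cost is SAP wording and revised table shells, with no new data. The downside is two summary scales, difference and ratio (or percent), in the laboratory tables. Step 1 alone removes the contradiction. Steps 2 to 4 give skewed analytes a relative summary without the upward bias and settle the zero-baseline gap.
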